12.3 Data safety and monitoring plan: The Principal Investigator will conduct a review of all adverse events and determine the attribution and grade of severity of the adverse event by using the following scales:

Attribution of Risk Categories:

Definite: Adverse event(s) will clearly be related to investigational agent(s) or other intervention

Probable: Adverse event(s) will likely be related to investigational agent(s)

Possible: Adverse event(s) may be related to investigational agent(s)

Unlikely: Adverse event(s) will doubtfully be related to investigational agent(s)

Unrelated: Adverse event(s) will clearly not be related to the investigational agents(s)

Grades of Risk:

0: No adverse event or within normal limits

1: Mild adverse event

2: Moderate adverse event

3: Severe adverse event resulting in hospitalization or prolongation of existing hospitalization, a persistent or significant disability/incapacity, or a congenital anomaly/birth defect

4: Life-threatening or disabling adverse event

5: Fatal adverse event

Serious adverse events (SAEs) include any untoward medical occurrence that at any dose results in death or the immediate risk of death, hospitalization or the prolonging of an existing hospitalization, persistent or significant disability/incapacity or a congenital anomaly/birth defect. Subjects will be terminated from participation if the investigator feels that subjects' health or well-being may be threatened by continuation in the study. Serious unanticipated and anticipated adverse events will be reported within 48 hours to the VA Hospital and Yale IRB, and NIDA. We will directly report to the FDA, whenever their magnitude or frequency exceeds expectations.

The risk associated with participating in this study is moderate, because nicotine administered may be associated with mild side effects. Serious adverse effects associated with nicotine infusion are not expected.

This project will be monitored by a Data and Safety Monitoring Board (DSMB) because the study involves double-blind treatment of smokers with nicotine. This board is composed of persons not otherwise affiliated with the clinical study who are experienced in various aspects of the conduct of clinical trials for the treatment of addictive disorders. The Yale TCORS Independent Data Safety Monitoring Board includes experts in the field of tobacco use behaviors and challenge studies (Chair: [name], FRCPC, Professor and Co-Director, Division of Brain and Therapeutics, Dept. of Psychiatry, U of Toronto; [name], Professor and Chair, Department of Health Outcomes & Behavior, H. Lee Moffitt Cancer Center & Research Institute) and statistics ([name], Associate Professor of Biostatistics, Columbia University). The members of the DSMB and all study Investigators will complete Conflict of Interest forms created by Yale's IRB in accordance with NIH guidelines.

In order for the DSMB to fulfill its mission of assuring the safety of human subjects and the scientific integrity of the studies conducted, the Board will have access to accumulating study outcome data in a manner that will protect its confidentiality and preserve its statistical integrity. The Board will examine accumulating data to assure that the risks and benefits of participation remain acceptable and that the results of the study will be considered scientifically reliable. The conditions under which the Board will examine this data are described below. This monitoring will be consistent with NIH policy regarding the protection of human subjects in research, and FDA guidance on statistical practices for clinical trials (ICH E9) and good clinical practices (ICH E6). In general, the data to be reviewed will include screening data, baseline data, efficacy data, and safety data.

The study will be monitored for safety in an ongoing way as well as three times each year formally by the DSMB. The P.I. will attend an initial part of this meeting to present the study's adverse events and ongoing subject accrual, as well as any potential study design changes under consideration. The remainder of the meeting will not include any direct study personnel until the end of the meeting, when the DSMB will convey directly to the P.I. any safety or study conduct concerns, as well as requests for potential interim analyses.

Following each DSMB meeting written minutes will be prepared and distributed summarizing any recommendations. These written reports will insure timely communication with the study P.I. with preparation of any protocol amendments necessary. After each DSMB meeting, this written report will describe all recommendations including additional safety steps.

The FDA adverse drug experience reporting timelines will be utilized as timelines to disseminate feedback from the DSMB to the principal investigator and sub investigators. That is, three days for acute circumstances and ten days for non-acute circumstances.

13. Informed consent: Subjects will be recruited from the New Haven area by newspaper advertisements and fliers. Interested subjects will be informed about the study over the telephone and asked for current use of drugs and medical problems. If subjects are interested, they will then come into the clinic for a full screening evaluation. Upon arrival, a research assistant will review the detailed consent form and will ask questions to make sure that the subjects understand the procedure and their rights and informed consent will be obtained.

14. Information Security/Confidentiality: Confidentiality in this study is of the utmost importance to us. All information obtained will be stored in coded form.

Personally identifiable information (PII) and protected health information (PHI) that is obtained from subjects or about them will be protected by the research team who will follow all guidance provided in the following VHA HANDBOOKS and DIRECTIVE:

- VHA HANDBOOK 1605.1, PRIVACY AND RELEASE OF INFORMATION Dated May 17, 2006
- VHA HANDBOOK 1907.01, HEALTH INFORMATION MANAGEMENT AND HEALTH RECORDS Dated August 25, 2006
- VHA HANDBOOK 6500, INFORMATION SECURITY PROGRAM Dated September 18, 2007
- MEMORANDUM FOR UNDER SECRETARIES, ASSISTANT SECRETARIES AND OTHER KEY OFFICIALS, SUBJECT: Protecting Information Security and Privacy Dated February 27, 2009
- VHA HANDBOOK 1200.12, USE OF DATA AND DATA REPOSITORIES IN VHA RESEARCH Dated March 9, 2009

All data collected will be the property of the Department of Veterans Affairs whether in paper or electronic form and will be secured utilizing the following methods:

Paper:

- All paper documents will be stored on VA property unless authorized by the Director, Information Security Officer, and Privacy Officer in writing.
- All paper documents will be locked in an approved file cabinet with only members of the research team having access.

Electronic:

- All information in electronic form will be stored on VA servers behind the VA firewall.
- All portable media will meet or exceed FIPS 140-2 compliance and encryption. And will be approved in writing by the Information Security Officer.

The location(s) where information will be stored is (are) Building 35, rooms 19 and 39
The people or agencies that will have access to the information are the study investigators.

No information related to this research will be released to any third party or disclosed outside of the VHA – except as required or permitted by law.

Research records will have identifiers removed and will be stored with a code number linked to subjects. The code will not be derived from any personal identifiers. The key to the code will be kept in a locked file cabinet, located in Bldg. 35, room 19. Subjects' identity will not be revealed in any reports or publications resulting from this study.

15. Location of Study: This study will be conducted in Ward G9W (the Biostudies Unit) located in Building 1 and in Bldg. 36 room 116 at the West Haven VA Medical Center.

16. Payment: Subjects will be paid cash; \$30 for participating in the screening, \$5.00 per phone call for approximately 28 phone calls, \$40 for each of the 2 outpatient visits and \$200 for each of the first test sessions and \$250 for the second test session. In addition, to help offset transportation costs, subjects will be paid \$40 for each of the 2 test sessions. If the subject is asked to return in addition to these visits for any reason, they will be paid \$20 for travel. If the subjects choose to terminate a session prematurely, or a session is terminated early for medical reasons, they will receive full payment for that day. If they become ineligible to continue in the study due to non-compliance with study procedures, they will only be paid for the portions of the study in which they have participated. Subjects may be paid up to \$700.00 if all parts of the study are completed. Payment may exceed \$700.00 if the subject is asked to return in addition for any reason. The payment will increase by \$20 for each additional visit.

Visits	Amount paid	Total
Screening Visit	\$30.00	\$30.00
Phone checks	\$5.00 per phone call or message	28 phone calls= \$140.00
Outpatient visits	\$40.00 each visit	2 outpatient visits: \$80.00

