Smokers will be recruited from the New Haven area through newspaper, and radio advertisements and fliers. The study will be described over the telephone. Subjects will be given a brief tobacco use history and medical screening questionnaire. Eligible subjects will be invited to a screening evaluation. The screening evaluation will include the following: a) obtaining an informed consent; b) tobacco use history, the Fagerstrom Test of Nicotine Dependence (FTND) and DSM-5 Tobacco Use Disorder (TUD) criteria; c) urine cotinine levels determined with a NicAlert test strip; d) complete physical and psychiatric examination including the structured clinical interview (SCID) for DSM-5 criteria; e) laboratory examination including CBC, TSH, ALT, AST, GGT, alkaline phosphatase, glucose, BUN and creatinine; f) urine analysis for drug screening, and for women, urine pregnancy test.

To minimize the risk of COVID-19 transmission, every attempt will be made to conduct the screening procedures that do not require in-person interaction, like physical and laboratory examination, remotely by video or phone. Consent form and other self-report forms will be mailed to the participants before the sessions and they will be asked to return these documents when they come to the medical center for screening.

Inclusion criteria: 1) Female and male smokers, aged 21 to 59 years, who have been smoking tobacco cigarettes for at least a year; 2) smoke ≥ 5 and less than 30 cigarettes per day; 3) urine cotinine levels > 100 ng/mL consistent with nicotine intake of an active smoker (23); 4) not seeking treatment at the time of the study for nicotine dependence; 5) in good health as verified by medical history, screening examination, and screening laboratory tests; and 6) for women, not pregnant as determined by pregnancy screening, nor breast feeding, and using acceptable birth control methods.

Exclusion criteria: 1) history of major medical or psychiatric disorders that the physician investigator deems as contraindicated for the subject to be in the study; 2) regular use of psychotropic medication (antidepressants, antipsychotics, or anxiolytics); 3) current alcohol or substance dependence for any other recreational or prescription drugs other than nicotine; 5) urine drug screening indicating recent illicit drugs use (with the exception of marijuana).

8: Recruitment:

Approximately, 50 subjects will be recruited, to have 38 completers.

9. Research Plan:

A) Measures

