The peak plasma concentrations of nicotine are expected to increase with increasing delivery rates of nicotine, as demonstrated in previous studies (28). In contrast, the AUC, which will include nicotine levels at time points before, during, and after nicotine delivery, reflects the total dose of nicotine independent of the delivery rate (74, 75). 3-hydroxycotinine is the main metabolite of cotinine and the ratio of 3HC/cotinine [nicotine metabolite ratio (NMR)], reflects the activity of cytochrome P450 (CYP) 2A6 and can therefore be used as a correlate of the rate of nicotine clearance (76). The NMR has been shown to be stable in smokers during ad lib and reduced smoking (77). Plasma samples for 3HC will be obtained at baseline and the NMR will be included as a covariate in our analyses. **Urine menthol glucuronide (MG):** In phase 1 and 2, urine samples will be obtained in the screening visit and before each test session to quantify MG levels at baseline and during study participation. In study 2, urine samples for MG will also be collected weekly to monitor compliance with switching to non-menthol cigarettes. **Alveolar carbon monoxide (CO):** The CO measurement taken before the sessions will help to verify compliance with smoking abstinence. Abstinence will be verified with CO or plasma nicotine as recommended by the SRNT Subcommittee on Biochemical Verification (56). The CO levels will be subsequently confirmed by the baseline nicotine levels, which will also account for all tobacco and nicotine product use. **Serum estradiol and progesterone analysis (females only):** Serum estradiol and progesterone levels will be collected before each test session for use as covariates in our analysis, since female sex hormones may contribute to sex differences in nicotine responses (54).

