Nicotine administration: Nicotine bitartrate will be obtained from Interchem Corporation, Paramus, NJ, and solutions for IV injection will be prepared by U.S. Specialty Formulations, Bethlehem, PA. On the morning of each test session, weight-adjusted nicotine and saline solutions will be prepared by the West Haven VA research pharmacy. Nicotine and saline will be administered using an infusion pump connected to an IV catheter located in a forearm vein. We have followed these procedures in our previous studies, which were completed without any serious adverse effects attributed to nicotine or other safety concerns. [name] holds an ITP (Investigational Tobacco Product) for IV nicotine administration. A new ITP application has been submitted to the FDA for this project.

In each test session, there will be a total of 3 infusions. Each infusion duration will be 10 minutes long, which will be achieved by infusing saline for the remainder of the time following the 2.5- and 5-minute nicotine infusions. A research nurse, will program 2 infusion pumps to administer nicotine or saline solutions. For the 2.5 and 5 min infusion conditions, participants will first receive nicotine for 2.5 and 5 minutes, followed by saline infusions. For the saline condition, participants will receive saline for 10 minutes. The participants will be blind to the randomization. The order of infusions will be: 1) 5-min or 2.5-min nicotine infusion, 2) saline infusion and 5-min or 2.5-min infusion. This infusion order was chosen to minimize carry over effects between nicotine infusions. Participants will be blind to the order of nicotine infusions.

Justification for the nicotine doses and infusion rates: The total nicotine dose for each test session will be 2 mg/70 kg body weight, a dose within the range of nicotine delivered by smoking 1 or 2 tobacco cigarettes or e-cigarettes (21). For safety reasons, the maximum dose of nicotine for each infusion will be 1 mg. The infusion rates will be 0.096 and 0.048 $\mu\text{g}/\text{kg}/\text{second}$ over 2.5 and 5 minutes, respectively.

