Menthol and Non-Menthol Cigarettes: Participants will be provided with free cigarettes in Phases 1 and 2 of the study. For the menthol condition, participants will be provided their usual brand of menthol cigarettes and for the non-menthol condition, they will be provided a matched-brand non-menthol cigarette (e.g., Newport Non-Menthol Gold 100s for those who smoke Newport Menthol Gold 100s). Participants will be given a two-week supply of their assigned cigarettes based on their reported cigarettes per day. If they run out of cigarettes earlier than expected, they will be given additional cigarettes not to exceed 20 % higher than the reported daily cigarette use.

Justification for age criteria: The study will enroll young adults between the ages of 21 to 59 because this age group captures the majority of smokers who smoke menthol cigarettes . Limiting enrollment to this age group will also minimize variation in the number of years of smoking that can influence measures of dependence, including withdrawal severity. The lower age limit is 21 because purchasing cigarettes below this age is illegal in Connecticut.

C) Study procedures

General procedures: Before the test sessions, smokers will be required to abstain from smoking for 10 h, which will be verified by expired air CO levels ≤ 8 ppm (56). Participants will be asked to refrain from consuming alcoholic beverages and drugs during study participation, which will be verified by urine drug screening and breathalyzer measurements before the

sessions. In our prior studies, the adherence rate with overnight abstinence has been over 95 percent. If results indicate non-adherence with these study procedures, the session will be rescheduled. Repeatedly non-adherent participants will be discharged from the study. Participants will be instructed to drink their typical number of caffeinated beverages in the morning to minimize caffeine withdrawal that could confound interpretation of study outcomes. Participants will be instructed not to eat for 4 hours before the sessions to minimize heartburn or nausea that can be associated with IV nicotine administration.

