Medical monitoring: Participants will be given a thorough physical examination prior to study entry. For nicotine administration sessions, participants will be attached to a cardiac monitor as well as a blood pressure and heart rate monitoring device. An IV catheter for nicotine delivery will be in place throughout each test session. Participants will be administered nicotine only if the systolic blood pressure is <150 mmHg and heart rate is <90 beats/minute. Participants will be terminated from the study if the blood pressure at any time is >170/110 mm Hg, if the heart rate is >130 beats/min, or if they develop signs and symptoms consistent with nicotine toxicity. We have not encountered any cases of nicotine toxicity in our nicotine infusion studies. These study procedures were developed as part of our Investigational Tobacco Product (ITP) application to the FDA for IV nicotine.

Overview of the study: We propose a placebo-controlled study that will recruit male and female menthol nicotine dependent smokers. Following screening and evaluation as described above, eligible participants will be enrolled in the study which will last about 4 weeks. Eligible, participants will be randomized to menthol or non-menthol smoking condition for 2 weeks (Phase 1) and then will be switched to the alternative condition for another 2 weeks (Phase 2). The smoking condition will be open label. Participants will be provided with free cigarettes in Phases 1 and 2. For the menthol condition, participants will be provided their usual brand of menthol cigarettes and for the non-menthol condition, they will be provided a matched-brand non-menthol cigarette (e.g., Newport Non-Menthol Gold 100s for those who smoke Newport Menthol Gold 100s). In week 2 of each Phase, participants will have a test session. Each session will include 3 infusions in the following order: nicotine (1 mg per 70 kg body weight to a maximum dose of 1 mg) delivered over 2.5 or 5 minutes, saline delivered over 10 minutes, and nicotine (1 mg/ 70kg to a maximum dose of 1 mg) delivered over 2.5 or 5 minutes). For safety reasons, the maximum dose of nicotine for each infusion will be 1 mg. The infusion rates will be 0.096 and 0.048 µg/kg/second over 2.5 and 5 minutes, respectively. Once the participants complete the test session, participants will be crossed over to the alternative treatment. The period between the 2 Phases will not be longer than one week.

Table 1: Study Overview

Procedures	Study Phases	

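### The document names a pregnancy test only at screening, and none before the IV nicotine sessions, although session 2 falls 22 to 35 days after Phase 1 Day 0

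*Combined protocol and SAP*

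**What the plan says.** At the screening evaluation (section 7, Subjects), item f is "urine analysis for drug screening, and for women, urine pregnancy test". Inclusion criterion 6 then requires, "for women, not pregnant as determined by pregnancy screening, nor breast feeding, and using acceptable birth control methods".

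After screening, the places where a repeat test could appear read as follows.

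- **Pre-session checks** (section 9, C, General procedures): expired CO for smoking abstinence. Abstinence from alcohol and drugs is a separate item, "which will be verified by urine drug screening and breathalyzer measurements before the" sessions.
- **Conditions for infusion** (Medical monitoring): "Participants will be administered nicotine only if the systolic blood pressure is <150 mmHg and heart rate is <90 beats/minute". Section 12 (Safety) repeats the same two limits.
- **Day 1 outpatient visits**: CO, urine cotinine, urine menthol glucuronide, questionnaires, heart rate and blood pressure, and the adverse-event checklist.
- **Table 2, baseline row**: CO, unspecified urine and blood samples, vital signs, questionnaires and the cognitive test.
- **Samples taken only from women** (section 9, A, Biomarkers): "Serum estradiol and progesterone levels will be collected before each test session for use as covariates in our analysis".

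Urine is in hand at each session, because for menthol glucuronide (MG) "urine samples will be obtained in the screening visit and before each test session to quantify MG levels at baseline" and during participation.

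On timing, Table 1 gives each phase as Days 0 to 14 with one session between Days 8 and 14. The Overview of the study limits the gap between phases to one week.

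**The concern.** Pregnancy status can change between screening and infusion, and the written plan has no step that would detect the change. Item f at screening pairs the drug screen with the pregnancy test. The drug screen is repeated before sessions, the pregnancy test is not, and no reason is given. Section 12 relies on screening to keep out subjects at greater risk, which works less well for a condition that can arise in the following weeks. Section 12.3 lets the investigator terminate a subject whose health may be threatened, but that power cannot act on a pregnancy nobody has detected.

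At stake is the safety of a small number of women, and any fetus, who would receive a research infusion with no direct benefit to them. No estimand, power figure or primary analysis depends on this.

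**Working it through.** **1. Age of the screening result.** Inputs: phase length 14 days and session on Days 8 to 14 (Table 1); gap 0 to 7 days (Overview of the study). The plan's own figure comes out first: 14 + 14 = 28 days, which matches its statement of about 4 weeks.

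- Session 1: Day 8 to Day 14.
- Session 2, no gap: 14 + 0 + 8 = Day 22 to 14 + 0 + 14 = Day 28.
- Session 2, one-week gap: 14 + 7 + 8 = Day 29 to 14 + 7 + 14 = Day 35.

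Session 2 therefore falls on Day 22 to Day 35. If Phase 2 Day 0 is the day after Phase 1 Day 14, the range is 23 to 36. Crossing over on the day of session 1 would allow Day 16 (8 + 8), but that contradicts the stated two-week phases. The screening result is older than these figures by the screening-to-Phase 1 lag, which the document does not limit.

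**2. Number of women.** Section 8 says: "Approximately, 50 subjects will be recruited, to have 38 completers". The Rationale for sample size instead has 30 individuals from about 38 recruited (30 / 0.8 = 37.5). The two do not agree, so both completer counts are shown. The share of women is assumed to match the preliminary study, 13 of 57, with one half as a higher case.

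- 30 × 13/57 = 6.8
- 38 × 13/57 = 8.7
- 38 × 0.5 = 19

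**3. Expected pregnancies before session 2.** Assumptions not in the documents: annual contraceptive failure f of 1% to 10%, and a urine test that turns positive 10 to 14 days after conception.

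Expected = women × [1 − (1 − f)^(d/365)]

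Two windows d are counted:

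- Conceived after Day 0 and detectable at session 2: 22 − 14 = 8 days to 35 − 10 = 25 days.
- Full interval from Day 0 to session 2, as a rough allowance for conceptions too early to show at screening: 22 to 35 days.

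| Women | Detectable window (f = 1%, d = 8; f = 10%, d = 25) | Full interval (f = 1%, d = 22; f = 10%, d = 35) |
|---|---|---|
| 6.8 | 0.0015 to 0.049 | 0.004 to 0.069 |
| 8.7 | 0.0019 to 0.062 | 0.005 to 0.087 |
| 19 | 0.004 to 0.137 | 0.012 to 0.191 |

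For session 1 the detectable window after Day 0 is at most 14 − 10 = 4 days, giving 0.010 for 8.7 women at f = 10%. The unknown screening lag would add to this.

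The direction of error is mixed. Enrolment to age 59 includes women who cannot conceive, so the counts lean high. Leaving out the screening lag makes them lean low.

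**4. Dose in context.** The session total is described as "a dose within the range of nicotine delivered by smoking 1 or 2 tobacco cigarettes or e-cigarettes". Two sessions are thus about 2 to 4 cigarettes. At the lower limit of 5 per day, 28 days is 140 cigarettes, so the share is 2/140 = 1.4% to 4/140 = 2.9%. At 29 per day it is 812 cigarettes, a share of 0.2% to 0.5%.

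**The case against.** The strongest case against is that this is an optional safeguard. Birth control is required at entry. Participants smoke 5 to 29 cigarettes a day whether or not they are infused. Each session also follows 10 hours of abstinence and lasts about three hours, so the infusion partly replaces that morning's smoking. All of this stands, and it keeps the marginal risk very small.

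The lists searched are also not complete checklists. The blood pressure and heart rate limits are necessary conditions, not a full set, and Table 2 omits the drug screen and breathalyzer too. That also stands, but those two checks are named under General procedures, whereas a repeat pregnancy test is named nowhere.

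A reader might infer three stronger things that the documents do not support.

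- **That inclusion criterion 6 is breached.** It is an entry criterion, and the screening test satisfies it.
- **That no repeat test is done.** The ITP application and the consent pages are not available here, and the safety procedures are said to have been developed as part of the ITP. The supportable claim is only that this document names no repeat test.
- **That the results are threatened.** Nothing in the analysis turns on it.

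One might also want breast feeding re-checked. A woman neither pregnant nor breast feeding at screening could not realistically start within about five weeks, so that adds nothing.

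**Conclusion.** The gap is real on the text. The only pregnancy test named precedes session 2 by at least 22 to 35 days, and a woman who conceives after screening could meet every written condition and be infused. The estradiol and progesterone samples do not close the gap: they are analysis covariates, and no result from them stops an infusion.

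Its size is small. The expected number of pregnancies is about 0.002 to 0.2 for the whole trial, depending on the number of women and the window counted. That range rests on the assumed failure rate, detection lag and share of women, but every combination shown is well below one. The timing itself rests only on the plan's calendar. The change is worth making because it is a participant-safety check at almost no cost. Confidence is medium, since a repeat test may be described in documents not seen here.

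**What to change.** For women of childbearing potential, run a urine pregnancy test on the urine already collected before each test session. Require a negative result before infusion 1, alongside the blood pressure and heart rate limits. If the result is positive: give no infusion, tell the participant privately, withdraw her and refer her for care.

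Name the test in General procedures, Medical monitoring, section 12 (Safety) and the baseline row of Table 2. If it is already done under the ITP, state it in those places and nothing else need change.

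The cost is two strips per woman who reaches both sessions (8.7 × 2, about 17, for 38 completers at the assumed share), an occasional cancelled session or withdrawal, and short text edits. It needs no extra visit, staff or invasive procedure. Under the assumed detection lag, conceptions in the last 10 to 14 days before a session would still be missed.
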